5.1 Agent Administration

Reported adverse events and potential risks are described in [Section 7](#). Appropriate dose modifications are described in [Section 6](#). No investigational or commercial agents or therapies other than those described below may be administered with the intent to treat the patient's malignancy.

Regimen Description					
EXPERIMENTAL ARM					
Agent	Premedications; Precautions	Dose	Route	Schedule	Cycle Length
Atezolizumab	antihistamines or antipyretics/ analgesics ¹	1200 mg	IV	Day 8 of Cycle 1 (28-day cycle) and Day 1 of Cycle 2+ (21-day cycles)	Cycle 1: 28 days Cycle 2+: 21 days
IL-7 (CYT107)²	None	10 mcg/kg	IM	Days 1, 8, 15 and 22 of Cycle 1 only	
CONTROL ARM					
Atezolizumab	antihistamines or antipyretics/ analgesics ¹	1200 mg	IV	Day 1 of each cycle	21 days

Note: ¹Premedication *not* permitted for the first dose on either arm; ²Calculate the required dose amount (10 mcg/kg) based on patient's baseline weight. The dose amount should be recalculated if the patient's weight changes by more than 10% from the baseline weight measurement.

5.1.1 *Atezolizumab*

All patients enrolled into this study will receive atezolizumab. Atezolizumab will be administered on Day 1 of each 21-day cycle in the control arm. Atezolizumab will be administered on Day 8 of Cycle 1 (28-day cycle) and on Day 1 of each subsequent cycle (21-day cycle) on the experimental arm. Atezolizumab may be administered up to 2 days before or after the scheduled administration date of each cycle due to administrative reasons.

Administration of atezolizumab will be performed in a setting with emergency medical facilities and staff who are trained to monitor for and respond to medical emergencies.

Atezolizumab will be administered following the CYT107 injection on Day 8 of Cycle 1 for patients enrolled in the Safety Run-in Phase and experimental arm.

For anaphylaxis precautions, see the management guidelines below. Atezolizumab infusions will be administered per the instructions outlined in the Table below.

First Infusion	Subsequent Infusions

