10. STUDY CALENDAR

Baseline evaluations are to be conducted within 14 days before the initiation of study treatment. Scans and x-rays must be done <4 weeks (28 days) before the initiation of study treatment. In the event that the patient's condition is deteriorating, laboratory evaluations should be repeated within 48 hours before the initiation of the next cycle of therapy. Patients receiving atezolizumab will be assessed for pulmonary signs and symptoms throughout the study.

SAFETY RUN-IN/EXPERIMENTAL ARM																				
Treatment Cycle		Cycle 1				Cycle 2				Cycle 3				Subsequent Cycle (Repeat up to 2 year)			End of Tx	Post-Treatment Follow-up		
Weeks	Screening visit	Wk1 ^a	Wk2	Wk3	Wk4	Wk5	Wk6	Wk7	Wk8	Wk9	Wk10	Wk11	Wk12	Wk13	At time of D/C ± 5 days	Safety FU	Disease Assessment ^f	Survival FU		
	Within 14 days	Day 1 ± 2	Day 8 ± 2	Day 15 ± 2	Day 22 ± 2	Day 1 ± 2	Day 8 ± 2	Day 15 ± 2	Day 1 ± 2	Day 8 ± 2	Day 15 ± 2	Day 1 ± 2	Day 8 ± 2	Day 15 ± 2		30 days ± 5 post DC	Every 12 ± 1 weeks	Every 12 ± 1 weeks		
Atezolizumab		A			A			A			A									
CYT107		B	B	B	B															
Administrative procedures																				
Informed consent	X																			
Demographics	X																			
Medical history	X																			
Concurrent meds	X	X-----				-----X				-----X				X	X	X	X			
Clinical Procedures/Assessments																				
Physical exam	X	X				X			X			X			X	X				
Vital signs ^b	X	X	X	X	X	X			X			X			X	X				
Height	X																			
Weight	X	X	X	X	X	X			X			X			X	X				
Adverse event evaluation		X-----				-----X				-----X				X	X	X				
Immune-related AEs evaluation		X-----				-----X				-----X				X	X	X				
Performance status	X	X	X	X	X	X			X			X			X	X				
EKG (as indicated)	X																			
Laboratory Assessments (Safety Labs)																				
CBC w/diff, plt	X	X	X	X	X	X			X			X			X	X				
Serum chemistry ^c	X	X	X	X	X	X			X			X			X	X				
Pregnancy Test (Urine or Serum HCG)	X ^d														X					
Efficacy Measurements																				
Tumor measurements	Within 28 days	Tumor measurements are repeated every 9±1 weeks . Documentation (radiologic) must be provided for patients removed from study for progressive disease.												X		X				
Radiologic evaluation ^k	Within 28 days	Radiologic measurements should be performed every 9 ± 1 weeks .												X		X				

SAFETY RUN-IN/EXPERIMENTAL ARM																				

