11. MEASUREMENT OF EFFECT

11.1 Antitumor Effect – Solid Tumors

For the purposes of this study, patients should be re-evaluated for response every 9 weeks.

Response and progression will be evaluated in this study using the new international criteria proposed by the revised Response Evaluation Criteria in Solid Tumors (RECIST) guideline (version 1.1) [[Eisenhauer 2009](#)]. Changes in the largest diameter (unidimensional measurement) of the tumor lesions and the shortest diameter in the case of malignant lymph nodes are used in the RECIST criteria.

This study will also evaluate response and progression using immune-related response criteria (irRC) [[Wolchok 2009](#)]. See [Appendix C](#) for a detailed description of the evaluation criteria.

11.1.1 *Definitions*

Evaluable for toxicity. All patients will be evaluable for toxicity from the time of their first treatment with atezolizumab and/or CYT107.

Evaluable for objective response. Only those patients who have measurable disease present at baseline, have received at least one cycle of therapy, and have had their disease re-evaluated will be considered evaluable for response. These patients will have their response classified according to the definitions stated below. (Note: Patients who exhibit objective disease progression before the end of cycle 1 will also be considered evaluable.)

Evaluable Non-Target Disease Response. Patients who have lesions present at baseline that are evaluable but do not meet the definitions of measurable disease, have received at least one cycle of therapy, and have had their disease re-evaluated will be considered evaluable for non-target disease. The response assessment is based on the presence, absence, or unequivocal progression of the lesions.

11.1.2 *Disease Parameters*

Measurable disease. Measurable lesions are defined as those that can be accurately measured in at least one dimension (longest diameter to be recorded) as ≥ 20 mm (≥ 2 cm) by chest x-ray or as ≥ 10 mm (≥ 1 cm) with CT scan, MRI, or calipers by clinical exam. All tumor measurements must be recorded in millimeters (or decimal fractions of centimeters).

Note: Tumor lesions that are situated in a previously irradiated area might or might not be considered measurable.

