11.1.6 Progression-Free Survival

PFS is defined as the duration of time from start of treatment to time of progression or death, whichever occurs first.

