13.5 Analysis of Secondary Endpoints

13.5.1 Secondary Objectives

Statistical analyses will be conducted for the following secondary objectives:

- The CBR, PFS, DOR, as measured by RECIST v1.1 and irRC, and OS.
- The CBR, PFS, DOR, and OS in patients stratified by PD-L1 expression levels in the tumor microenvironment, as assayed by Genentech.

The CBR is defined as the percentage of patients with advanced or metastatic cancer who have achieved CR, PR, and SD to a therapeutic intervention in clinical trials of anticancer agents. A two-sided test for a difference in proportions will be conducted to compare the CBR in the experimental arm to the CBR in the control arm. A two-sided significance level of 0.05 will be considered for the test.

The PFS, DOR, and OS will be summarized using Kaplan-Meier estimates. Long-rank tests will be conducted for OS and PFS to compare between the 2 arms. A one-sided significance level of 0.10 will be considered.

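### With a 28-day first cycle in one arm only and a scan schedule not separated from dosing visits, the PFS log-rank test can be biased towards CYT107 if sites tie scans to dosing

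*Combined protocol and SAP*

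**What the plan says.** Section 5.1.1 gives the two schedules. Control: "Atezolizumab will be administered on Day 1 of each 21-day cycle in the control arm". Experimental: "Atezolizumab will be administered on Day 8 of Cycle 1 (28-day cycle) and on Day 1 of each subsequent cycle (21-day cycle". It also allows some slack: "Atezolizumab may be administered up to 2 days before or after the scheduled administration date of each cycle due to administrative reasons".

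Imaging is written in weeks and is the same in both arms. Each arm's calendar in Section 10 says "Radiologic measurements should be performed every" 9±1 weeks, and Section 11.1 says "patients should be re-evaluated for response every 9 weeks". Neither gives a starting point for the count (randomization, Cycle 1 Day 1, first atezolizumab dose or previous scan). Neither says that the count ignores cycle number and dose delays.

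The PFS clock is common to both arms. Section 11.1.6: "PFS is defined as the duration of time from start of treatment to time of progression or death, whichever occurs first". Treatment starts on Cycle 1 Day 1 in both arms, with CYT107 in the experimental arm and atezolizumab in control. Section 13.5.1 then states "Long-rank tests will be conducted for OS and PFS to compare between the 2 arms" and "A one-sided significance level of 0.10 will be considered". No dating to scheduled visits, interval-censored test or sensitivity analysis for assessment timing is specified. The opening of Section 13 says that no separate SAP will be issued.

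**The concern.** Most progressions are found at scans, so recorded progression dates cluster at scan dates. The log-rank test uses only the order of the times. If one arm is scanned systematically a week later on the same clock, control progressions are counted while the matching experimental patients still appear progression-free. The test reads that as longer PFS.

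Nine weeks is exactly three 21-day cycles, so scanning just before the Cycle 4 dose is a natural site habit. In control that dose falls at 9 weeks, and in the experimental arm at 10. The plan does not rule the habit out. At stake is a named secondary comparison, in an open-label trial, tested at a lenient one-sided 0.10.

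**Working it through.** **Visit days.** From Section 5.1.1, with k the cycle number (k ≥ 2):

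- Control, Cycle k Day 1 = 1 + 21(k − 1): Day 64 for k = 4, Day 127 for k = 7.
- Experimental, Cycle k Day 1 = 1 + 28 + 21(k − 2): Day 71 for k = 4, Day 134 for k = 7.

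The difference is 7 days at every cycle from the second on. The ±2-day dosing window narrows this for individuals but does not absorb it. Control Cycle 4 may be dosed on Days 62–66 and experimental Cycle 4 on Days 69–73.

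**Compliance.** Counted from Day 1, a first scan at 63 ± 7 days falls on Days 57–71. Day 64 and Day 71 both comply. Counting nine weeks from the first atezolizumab dose, which the text does not exclude, gives the same pair: 1 + 63 = Day 64 and 8 + 63 = Day 71.

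**Design inputs.** Section 13.3 gives 24 per arm and one-sided alpha 0.10. The plan states no power, event count or effect size for PFS, so there is no PFS figure to reproduce. As a check on the inputs, its ORR power (14.8% against 45%) with unpooled variance is Φ(0.302 / √[(0.148×0.852 + 0.45×0.55)/24] − 1.2816) = Φ(2.42 − 1.28) = 87.3%, close to the stated 88%.

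**Direction, by hand.** Take identical exponential PFS with median 9 weeks, no deaths, control scanned at week 9 and experimental at week 10.

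- Week 9: 24 × 0.5 = 12 control events, with 24 at risk in each arm. Experimental: observed 0, expected 12 × 24/48 = 6.
- Week 10: 24 × (1 − 2^(−10/9)) = 12.9 experimental events, with 24 experimental and 12 control at risk. Expected in the experimental arm: 12.9 × 24/36 = 8.6.
- Observed minus expected, experimental = 12.9 − (6 + 8.6) = −1.7.

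Had both arms been scanned at week 9, it would be 12 − 12 = 0. The lag alone moves the statistic towards CYT107.

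**Size, by simulation.** Set-up: 24 per arm; identical true exponential PFS; progression dated at the first scan after it occurs; deaths dated exactly; censoring at 104 weeks; one-sided 0.10. Median PFS and the share of deaths are not in the documents and are assumed. The table takes the extreme case, with control scans at exactly 9, 18, 27, … weeks and experimental scans at 10, 19, 28, … weeks (1,500 runs per scenario, 2,000 for the last column; Monte Carlo standard error about 0.01). Entries are false-positive rates with 0% / 20% of events being deaths.

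| Median PFS | Same schedule | All experimental patients one week late | Half of experimental patients late | All late, events dated to scheduled visit |
|---|---|---|---|---|
| 9 weeks | 0.11 / 0.11 | 0.49 / 0.34 | 0.20 / 0.16 | 0.07 / 0.09 |
| 13 weeks | 0.10 / 0.12 | 0.34 / 0.23 | 0.17 / 0.15 | 0.08 / 0.09 |
| 22 weeks | 0.10 / 0.12 | 0.22 / 0.16 | 0.13 / 0.11 | 0.08 / 0.09 |

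A more realistic set-up applies the ±2-day dosing window and varies the share of patients whose scans are tied to dosing. Across medians of 9–26 weeks and 0–20% deaths it gives:

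- all tied: 14–40%
- half tied: 11–21%
- none tied: 10–12%
- all tied, events dated to the scheduled visit: 7–11%

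The distortion is in the test statistic. In the extreme case the simulated median PFS differed between arms by about half a week or less, sometimes in control's favour, so comparing medians would not reveal it.

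**The case against.** The strongest reply is that the plan does not schedule any lag. The scan interval is written in weeks and is identical in both arms. Where the protocol wants a procedure tied to a cycle it says so, as with the biopsy before Cycle 4 Day 1 dosing (Section 5.1.3) and the microbiome kits at Cycle 3 Day 1 (Section 5.1.4). Sites that count nine weeks from treatment start in both arms produce no bias. This stands: the lag is permitted, not required, and the biopsy timing is at most circumstantial evidence of how sites will book scans.

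A reader might infer that scan windows tied to dosing cannot overlap between arms, so that every control scan event precedes its experimental counterpart. The documents do not support that. With control dosed on Day 66 and experimental on Day 69, the preceding weeks are Days 59–66 and 62–69, which share Days 62–66.

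The largest rates are corner cases. They need every patient affected at every scan, a 9-week median and no deaths as PFS events. Section 2.4 cites a median OS of 7.9 months and Section 3.1.5 admits ECOG 2, so some deaths as events are likely. With half of patients tied and 20% deaths, rejection is 18%, 16% and 13% at medians of 9, 13 and 26 weeks; with 40% deaths it is 15%, 13% and 12%. End-of-treatment scans, 12±1-week assessments after treatment and atezolizumab holds of up to 84 days were not modelled and would loosen the tie.

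None of this restores the stated test. It rejects at its nominal level only if site practice happens to be the same in both arms, and nothing in the plan secures that.

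**Conclusion.** The point holds as a conditional weakness of a secondary analysis. The one-week offset in dosing visits, the missing scan origin and the actual-date log-rank test are all in the text. Whether scans follow dosing visits, and for how many patients, is an assumption, as are median PFS and the share of deaths. On those assumptions the 10% test rejects about 14–40% of the time under full tying and 11–21% if half of patients are tied, and there is no inflation attributable to the lag if none are.

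A reader might go further and conclude that a positive PFS result would be an artefact, or that the trial's main conclusion is at risk. Neither follows. The primary ORR test does not use event times, and the plan attaches no decision rule to PFS. The case for acting is that the remedy is cheap and the analysis part works whatever sites do, whereas unequal scan timing cannot be fully repaired afterwards.

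**What to change.** 1. **Section 13.5.1 (main remedy).** Specify a PFS log-rank test with each event assigned to its scheduled 9-week assessment interval from Day 1 (scan-detected progressions to weeks 9, 18, 27, …; deaths to the end of the interval in which they fall), or an interval-censored log-rank test. It should be at least a prespecified sensitivity analysis beside the actual-date test. Keep actual dates for the Kaplan-Meier curves.
2. **Sections 10 and 11.1.** State that scans in both arms are targeted at weeks 9, 18, 27, … from Cycle 1 Day 1, regardless of cycle number or dose delay, with ±1 week as a tolerance only.

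The second change reduces the lag but does not remove it. A ±1-week tolerance around Day 64 is still Days 57–71, so control scans on Days 57–64 and experimental scans on Days 64–71 would all comply. That is why the first change matters more.

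The cost is a few sentences, with no extra scans and no change to dosing. The PFS test becomes slightly coarser and, if the lag does occur, slightly conservative for CYT107 (7–11% against a nominal 10%).

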5.1.2 Recombinant Human IL-7 (CYT107)

Patients enrolled in the Safety Run-in phase and patients randomly assigned to the experimental arm of the trial will receive recombinant human IL-7 (CYT107). The patients will receive 10 mcg/kg of IL-7 (CYT107) IM on days 1, 8, 15 and 22 of Cycle 1 only. The CYT107 dose must be administered before atezolizumab on Day 8 of Cycle 1.

For patient with a Body Mass Index (BMI) >30, an adjusted body weight will be used to calculate the final dose the patient will receive. Please refer to [Appendix D](#) for details on the adjusted body weight calculation.

Patients receiving CYT107 will have their vital signs (heart rate, respiratory rate, blood pressure, and temperature) determined within 60 minutes before the first CYT107 injection on day 1, and 2 hours (\pm 15 minutes) after the injection.

On day 8, vital signs will be monitored as described above ([Section 5.1.1](#)) following the guidelines for the first atezolizumab infusion.

On days 15 and 22, vital signs will be determined within 60 minutes before and within 30 minutes after the injection.

Patients will be informed about the possibility of the development of an allergic reaction to CYT107 (hives, bronchospasm, rash, etc.) and instructed to contact their study physician if they develop such symptoms.

5.1.3 Other Procedures: Biopsy (core needle, punch or excisional)

The rationale for the biopsy/tissue collection is to investigate changes in the tumor microenvironment that may correlate with response or provide information on potential actionable causes for lack of benefit.

A pre-treatment biopsy/tissue collection will be obtained before the first dose of study treatment (atezolizumab or CYT107) assuming this can be carried out safely.

Note: If an archival tumor sample (at least $0.5 \times 0.5 \times 0.5$ cm) obtained within 2 years from screening visit is available, the pre-treatment biopsy is not required.

A post-treatment tumor biopsy/tissue collection will be obtained if deemed relatively safe and technically feasible (core biopsy, punch biopsy or excisional biopsy). The tumor biopsy/tissue collection will be obtained prior to dosing on Cycle 4, Day 1 or at the end of treatment visit, whichever occurs first.

The biopsies will be done according to clinical site Standard Operating Procedures (SOPs).

5.1.4 Other procedures: Microbiome Sample Collection

Pre-treatment and post-treatment microbiome samples will be collected by patients using standard, at home stool-collection procedures using standardized fecal swab/storage devices. The samples will be stored frozen at home by patient and returned to the clinical research site at their next study visit.

Patients will be provided with fecal swab/storage devices and instructions (refer to [Appendix E](#)) at the screening visit and at the Cycle 3, Day 1 visit.

5.2 **Safety Run-in: Definition of Dose-Limiting Toxicity**

Dose-limiting toxicity is defined as any adverse event (AE) occurring within the first 28 days (*i.e.*, from Week 1 Day 1 through Week 4 Day 7), that is considered to be ***at least possibly related*** to the protocol treatment (atezolizumab, CYT107 or both), and that meets at least one of the non-hematologic or hematologic criteria below:

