5.2.1 Hematologic toxicity

The standard NCI Common Terminology Criteria for Adverse Events (CTCAE) v.5.0 criteria will be replaced by these criteria:

- Any Grade 4 event, including laboratory electrolyte abnormalities, that is not easily reversed without sequelae
- Grade 4 neutropenia (Absolute Neutrophil Count (ANC) $<0.5 \times 10^9/L$)
- Grade 3 febrile neutropenia (ANC $<1.0 \times 10^9/L$ with a fever $\geq 38.3^{\circ}C$)
- Grade 4 thrombocytopenia ($<25.0 \times 10^9/L$) lasting >4 days or that requires platelet transfusion
- Grade ≥ 3 thrombocytopenia ($<50.0-25.0 \times 10^9/L$) associated with Grade ≥ 3 bleeding
- Grade 2 concurrent AST or ALT $>3\times$ ULN and total bilirubin $>2\times$ ULN without evidence of cholestasis
- Any toxicity resulting in death (*i.e.*, Grade 5)

Note: Peripheral lymphocytopenia after the first CYT107 injection is not a sign of toxicity; it reflects the lymphocytes “homing effect” of *rhIL-7*. Lymphocyte counts usually come back to baseline 5 to 7 days after the first injection.

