5.2.2 Non-hematologic toxicity

Any Grade ≥ 3 non-hematologic toxicity (CTCAE v5.0), ***except*** for the following, which will not constitute DLTs:

- Grade ≥ 3 nausea or vomiting lasting ≤ 72 hours with the use of adequate/maximal medical intervention and/or prophylaxis

- Grade 3 diarrhea lasting \leq 72 hours with the use of adequate/maximal medical intervention and/or prophylaxis
- Grade 3 fatigue lasting \leq 7 days
- Grade 3 injection site reaction (unless operative intervention is required)
- Grade 3 hyperglycemia lasting \leq 72 hours with standard antidiabetic therapy
- Grade 3 increases in liver transaminases ($>5.0-20.0 \times$ ULN) in patient with liver metastases
- Clinical laboratory abnormalities that are reversible to \leq Grade 1 or baseline status within 72 hours with outpatient care and/or monitoring, or that are considered not clinically significant by the treating physician

Management and dose modifications associated with the above AEs are outlined in [Section 6](#).

The AEs will be assessed by the Toxicity Evaluation Committee, which includes the PI(s), study sponsor(s), CTEP and the CITN Central Operating and Statistical Center (COSC).

The patients must complete the full 4-week DLT window to be considered evaluable for DLTs. Patients who discontinue from the study before completion of the full 4-week DLT window for reasons other than the occurrence of a DLT (e.g., withdrawal of consent, rapid tumor progression, death due to rapid tumor progression, AE that does not meet DLT criteria) will not be considered evaluable for DLTs and will be replaced.

All randomly assigned patients will be monitored for occurrence of DLT. Monitoring of all safety and toxicity data is done by the PI, the study Sponsor(s) and the CITN COSC on a real-time basis as data are entered into Medidata Rave using the Web Reporting Module. All participating sites must notify the PI and CITN COSC when a DLT has occurred.

A delay due to toxicity in receiving the second cycle of therapy of >14 days will be considered a DLT in subjects enrolled in the safety run-in phase of the study. This does not apply to subsequent subjects enrolled in the randomized component of the study.

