7.1.1 CAEPRs for Atezolizumab (MPDL3280A, NSC 783608)

Below is the CAEPR for Atezolizumab. Frequency is provided based on 3097 patients.

Version 2.3, March 11, 2021¹

Adverse Events with Possible Relationship to Atezolizumab (MPDL3280A) (CTCAE 5.0 Term) [n= 3097]			Specific Protocol Exceptions to Expedited Reporting (SPEER)
Likely (>20%)	Less Likely (<=20%)	Rare but Serious (<3%)	
BLOOD AND LYMPHATIC SYSTEM DISORDERS			
	Anemia		
CARDIAC DISORDERS			
		Heart failure ²	
		Myocarditis ²	
		Pericardial effusion ²	
		Pericardial tamponade ²	
		Pericarditis ²	
ENDOCRINE DISORDERS			
		Adrenal insufficiency ²	
		Endocrine disorders - Other (diabetes) ²	
	Hyperthyroidism ²		
		Hypophysitis ²	
	Hypothyroidism ²		
EYE DISORDERS			
		Eye disorders - Other (ocular inflammatory toxicity) ²	
		Uveitis ²	
GASTROINTESTINAL DISORDERS			
	Abdominal pain		Abdominal pain (Gr 2)
		Colitis ²	
	Diarrhea		Diarrhea (Gr 2)
	Dysphagia		
	Nausea		Nausea (Gr 2)
		Pancreatitis ²	
	Vomiting		Vomiting (Gr 2)
GENERAL DISORDERS AND ADMINISTRATION SITE CONDITIONS			

Adverse Events with Possible Relationship to Atezolizumab (MPDL3280A) (CTCAE 5.0 Term) [n= 3097]			Specific Protocol Exceptions to Expedited Reporting (SPEER)
Likely (>20%)	Less Likely (<=20%)	Rare but Serious (<3%)	
Fatigue			Fatigue (Gr 2)
	Fever ³		
	Flu like symptoms ³		
HEPATOBILIARY DISORDERS			
		Hepatic failure ²	
		Hepatobiliary disorders - Other (hepatitis) ²	
IMMUNE SYSTEM DISORDERS			
	Allergic reaction ³		
		Anaphylaxis ³	
		Cytokine release syndrome ³	
		Immune system disorders - Other (systemic immune activation) ²	
INFECTIONS AND INFESTATIONS			
Infection ⁴			
INJURY, POISONING AND PROCEDURAL COMPLICATIONS			
	Infusion related reaction ³		
INVESTIGATIONS			
	Alanine aminotransferase increased ²		
	Alkaline phosphatase increased ²		
	Aspartate aminotransferase increased ²		
	Blood bilirubin increased ²		
		Creatinine increased	
	GGT increased ²		
	Lipase increased*		
		Platelet count decreased	
	Serum amylase increased*		
METABOLISM AND NUTRITION DISORDERS			
	Anorexia		Anorexia (Gr 2)
		Hyperglycemia ²	
	Hypokalemia		
	Hyponatremia		
MUSCULOSKELETAL AND CONNECTIVE TISSUE DISORDERS			
	Arthralgia ²		
	Back pain		
		Generalized muscle weakness	
	Myalgia		
		Myositis ²	
NERVOUS SYSTEM DISORDERS			
		Ataxia ²	
		Encephalopathy ²	
		Nervous system disorders - Other (encephalitis non-infective) ²	
		Guillain-Barre syndrome ²	

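### The run-in DLT window closes one day before the first planned safety labs after the fourth CYT107 dose

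*Combined protocol and SAP*

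**What the plan says.** - **Window.** Section 5.2 defines a DLT as an event at least possibly related to treatment that occurs in the first 28 days, "from Week 1 Day 1 through Week 4 Day 7".
- **Dosing.** Section 5.1.2 gives "10 mcg/kg of IL-7 (CYT107) IM on days 1, 8, 15 and 22 of Cycle 1 only".
- **Labs.** The run-in/experimental calendar in Section 10 has CBC and serum chemistry in each of Weeks 1 to 4, then at Week 5 (Cycle 2 Day 1, ±2 days), with nothing between. Section 5.1.1 allows the same tolerance for the infusion: "Atezolizumab may be administered up to 2 days before or after the scheduled administration date of each cycle". Section 10 also says "laboratory evaluations should be repeated within 48 hours before the initiation of the next cycle of therapy", but only for a patient whose condition is deteriorating.
- **Laboratory findings can be DLTs.** Section 5.2.1 lists "Grade 2 concurrent AST or ALT" above 3×ULN together with bilirubin above 2×ULN. Section 5.2.2 counts non-hematologic toxicity of grade 3 or higher. It exempts, among others, laboratory abnormalities that return to grade 1 or lower "or baseline status within 72 hours with outpatient care and/or monitoring".
- **Late criterion.** For run-in patients, Section 5.2.2 adds: "A delay due to toxicity in receiving the second cycle of therapy of >14 days will be considered a DLT".
- **Evaluability and decision.** Sections 5.2.2, 5.7 and 13.3 require completion of the 4-week window and name no closing lab. Under Sections 5 and 13.3, 0 or 1 DLT lets the trial proceed, and 2 or more suspend enrollment.

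**The concern.** The run-in exists to show that the full four-dose CYT107 course with atezolizumab is tolerable before randomization opens. Each of the first three CYT107 doses is followed by planned safety labs inside the window. The fourth, at nominal timing, is not. An abnormality without symptoms would normally be found at the Cycle 2 Day 1 draw, just after the window has closed, and no rule says how to date it.

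The DLT count decides whether patients 4 to 6 are enrolled and whether randomization begins. With six patients, one event separates proceeding from suspending, so the count should not rest on an unstated dating convention.

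**Working it through.** **1. The plan's own figures.** Week 4 Day 7 = 3×7 + 7 = Day 28, which agrees with the stated 28 days. The 16.7% in Section 13.2 is 1/6, which agrees with the rule that one DLT in six is acceptable.

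**2. Where the next labs fall.** Cycle 1 lasts 28 days (Section 5.1), so Cycle 2 Day 1 = 28 + 1 = Day 29. With ±2 days it may fall on Day 27, 28, 29, 30 or 31. Two of these five days are inside the window and three (29, 30, 31) are outside.

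**3. Lab cover by dose, nominal timing.**

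| CYT107 dose | Day | Next planned safety labs | Inside Days 1–28? |
|---|---|---|---|
| 1 | 1 | Day 8 | yes |
| 2 | 8 | Day 15 | yes |
| 3 | 15 | Day 22 | yes |
| 4 | 22 | Day 29 | no |

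After dose 4 the window has 28 − 22 = 6 days left (Days 23 to 28), with 0 planned safety labs. This takes the Day 22 draw as pre-dose. Section 6.2 implies that, since it requires lymphocyte recovery by the next weekly dose, but the calendar does not state it for the safety labs.

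**4. Does other text catch a Day 29–31 finding?**
- The repeat-lab rule does not, because a patient without symptoms is not deteriorating.
- The delay criterion catches longer toxicities. For example, under Section 6.1.2.2 a grade 2 hepatic event lasting more than 5 days leads to withholding and steroids, which must be tapered over at least a month before resumption. Two cases are less clear. The liver tests involved appear in Section 7.1.1 as possibly related to atezolizumab (for example "Alanine aminotransferase increased").
  - (a) The combined transaminase and bilirubin rise of Section 5.2.1, at grade 2 and lasting 5 days or less. Section 6.1.2.2 asks only for more frequent monitoring, so nothing there forces a delay.
  - (b) A grade 3 transaminase rise in a patient without liver metastases, clinically significant and not reversed within 72 hours. Section 6.1.2.2 calls for permanent discontinuation. The text does not say whether never receiving Cycle 2 is a delay.
- Where the criterion applies, it is slow. Day 29 + 14 = Day 43, so a delay of more than 14 days is first established on Day 44, 16 days after Day 28. The committee's decisions follow completion of the 4-week window.

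**5. Effect on the decision.** Let k be the number of other patients with a counted DLT, and suppose one event goes uncounted.
- k = 0: the true count is 1, and the run-in proceeds either way.
- k = 1: the true count is 2, and suspend becomes proceed.
- k ≥ 2: enrollment is already suspended.

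Only k = 1 matters.

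**The case against.** The strongest reply is that Section 5.2 speaks of events occurring, not events detected. An abnormality absent on Day 22 and present before dosing on Day 29 arose in between, and six of those seven days are in the window. Section 7.3.1 likewise collects adverse events by the period in which they start. The committee may therefore date a Day 29 finding to Day 28 or earlier. This stands. A reader might infer that the plan bars such a finding from the count. It does not. It leaves the matter open, and nothing requires the committee to count it.

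Other replies also hold in part:
- Section 7.3.5 requires expedited reporting of most events like case (a), and the committee, on which CTEP sits, reviews all adverse events. The event would be seen. The suspension rule, however, counts only protocol-defined DLTs.
- For CYT107, Section 7.1.2 lists ALT, AST and bilirubin increases under insufficient evidence of causation. Atezolizumab, given on Day 8, is followed by planned labs on Days 15 and 22. This weakens the link between the liver cases and dose 4. It does not remove it, because the risk lists for both agents warn that a combination may produce new events.
- Case (b) may already count if never receiving Cycle 2 is read as a delay of more than 14 days. That reading is natural but unstated.
- A window equal to the first cycle is a coherent choice. It holds all four CYT107 doses and 28 − 8 = 20 days after atezolizumab. The objection here is not to 28 days as such. It is that the cutoff falls just before labs that are already scheduled.

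**Conclusion.** The point holds in a limited form and merits a change, with medium confidence. At nominal timing the window shuts one day before the first planned labs after dose 4, and three of the five permitted days for those labs lie outside it. A patient can be cleared as evaluable and DLT-free without a planned lab after the last CYT107 dose.

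The exposure is small. Only dose 4 is affected. Cycle 2 Day 1 labs on Days 27–28, symptomatic in-window events and unscheduled in-window labs are all captured. A second DLT recognized later still suspends enrollment. One uncounted event matters only when k = 1. The conclusion assumes nominal timing, a pre-dose draw on Day 22 and no unscheduled labs.

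A reader might also infer that the chance of passing the run-in is inflated by a known amount. The documents do not support that: any figure would need the share of DLTs first appearing on Days 29–31, and none can be derived from them.

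**What to change.** In Section 5.2, define the run-in DLT window and evaluability as running through Day 28 or the Cycle 2 Day 1 pre-dose safety labs, whichever is later. Draw those labs by Day 31 even if Cycle 2 is delayed or stopped. Count any related abnormality found there that meets 5.2.1 or 5.2.2, leaving every 5.2.2 exception unchanged. Take the decisions after patients 3 and 6 once those results are in, and make Sections 5, 5.2.2, 5.7 and 13.3 conform.

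Do not add a blanket rule that permanent discontinuation before Cycle 2 is a DLT. It would turn events that 5.2.2 exempts, such as grade 3 injection site reactions or grade 3 transaminase rises with liver metastases, into DLTs, because Section 6 can take those patients off treatment. At most, state that never receiving Cycle 2 because of a related toxicity meets the delay criterion of more than 14 days, unless 5.2.2 expressly exempts the event.

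The visit and labs already exist. The cost is wording, about 1 to 3 extra days at each of the two decisions (31 − 28 = 3 at most), up to 72 hours more (to Day 34) if reversal must be observed, and an occasional replacement when a patient leaves after Day 28 but before the draw without a DLT. The change still misses an abnormality that arises and resolves between Day 22 and Cycle 2 Day 1.
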